10. Willingness to swallow pills and no medical condition that would interfere with this.
11. Male patient and his female partner who is of childbearing potential must use 2 acceptable methods of birth control (one of which must include a condom as a barrier method of contraception) starting at screening and continuing throughout the study period and for 3 months after final study drug administration. Patients are also required to use a condom if having sex with a pregnant woman.
12. Patient should agree to a tumor tissue biopsy prior to protocol enrollment. Post therapy biopsy is optional.
13. Patients who are being treated with a GNRH antagonist should be willing to switch to a LHRH analogue after registration.
14. Patients must have one of the following a) Low volume disease (defined as no visceral metastases and < 4 bone metastases) or b) are not candidates for docetaxel based chemotherapy or 3) refused docetaxel chemotherapy

4.2 Patients must NOT meet any of the following exclusion criteria:

1. History of seizure or any condition that may predispose to seizure (e.g., prior cortical stroke, significant brain trauma) at any time in the past. Also, history of loss of consciousness or transient ischemic attack within 12 months of Day 1 visit;
2. Known or suspected brain metastasis or active leptomeningeal disease;
3. Severe concurrent disease, infection, or co-morbidity that, in the judgment of the Investigator, would make the patient inappropriate for enrollment;
4. Absolute neutrophil count < 1,000/ μ L, or platelet count < 50,000/ μ L, or hemoglobin < 8 /dL) at the Screening visit.
5. Total bilirubin, alanine aminotransferase (ALT) or aspartate aminotransferase (AST) > 2.5 times the upper limit of normal
6. Creatinine > 177 μ mol/L (2 mg/dL)
7. Clinically significant cardiovascular disease including:
 - Myocardial infarction within 6 months;
 - Uncontrolled angina within 3 months;
 - Congestive heart failure New York Heart Association (NYHA) class 3 or 4, or patients with history of congestive heart failure NYHA class 3 or 4 in the past, unless screening echocardiogram or multi-gated acquisition scan performed within 3 months results in a left ventricular ejection fraction that is \geq 45%;

---History of clinically significant ventricular arrhythmias (e.g., ventricular tachycardia, ventricular fibrillation, torsades de pointes);

---History of Mobitz II second degree or third degree heart block without a permanent pacemaker in place;

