8.13 Circulating Tumor Cells Response

The outcome measures associated with this definition are the following:

Measurements of CTC counts pre-therapy, post-therapy and the change between time points. To assess the pre-therapy circulating tumor cell (CTC) counts and the changes in CTC after 1 month of therapy, and to associate them with the primary endpoint. CTC counts will be measured at baseline (day 1), and month 1 (days 28-42) of therapy. The pre and post-therapy CTC counts ; $<5/7.5$ ml which is considered favorable, vs $>5/7.5$ ml which is considered unfavorable, have been shown to be prognostic in metastatic CRPC patients treated with cytotoxic chemotherapy.

8.14 Correlative tests:

Androgen metabolism enzymes: ERG, CXCR4, Androgen biosynthetic enzymes: Testing will be conducted on paraffin embedded fixed tissue. Analysis will be performed by Immunohistochemistry. Scoring will be between 0 to 3 and will be done by 2 independent experienced investigators.

Androgen biosynthetic enzymes: ERG, CXCR4 testing is conducted on RNA from frozen tumor tissue biopsies. RNA message measurement by qualitative and quantitative RT- PCR (real time PCR). Qualitative Scoring for RT-PCR is the presence or absence of band (+/-) when an amplified PCR mixture is run on gel. Quantitative PCR is the level of expression of the test gene will be expressed in in terms of folds.

Genomic testing:

AR splice variants: Starting material is frozen tissue. Analysis is RNA message quantitation by RT-PCR and QPCR, which is similar to androgen biosynthesis analysis: Qualitative (+/-) and quantitative results (copy number) will be obtained.

9.0 CRITERIA FOR REMOVAL FROM STUDY:

- 9.1 Intercurrent illness which would, in the judgment of the investigator, a) affect assessments of clinical status to a significant degree, b) require discontinuation of drug, or c) both a and b.
- 9.2 Receiving any other treatment, investigational agent or alternative therapy directed at prostate cancer.
- 9.3 Unacceptable toxicity
- 9.4 Disease progression
- 9.5 Delay in treatment of \geq 2 months
- 9.6 The patient may withdraw from the study at any time for any reason.
- 9.7 In the judgment of the investigator, further treatment would not be in the best interest of the patient.

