11.2 Secondary Objectives:

- 1) To compare the primary endpoint by race (African American [AA] vs Other).
- 2) To compare the rates of each of 2 types of response by treatment arm:
 - a) Measurable disease response; and
 - b) PSA response.
- 3) To compare each of 7 time-to-event endpoints by treatment arm:
 - a) Duration of overall response (RD);
 - b) Duration of stable disease (SDD);
 - c) Time to treatment failure (TTF);
 - d) time-to-progression (TTP);
 - e) TTP in patients with bone metastases;
 - f) progression-free survival (PFS); and
 - g) Overall survival (OS).
- 4) To compare the rates of each type of toxicity by treatment arm.
- 5) To compare the incidence rate of skeletal related events (SRE), and the time until SRE, separately by treatment arm.
- 6) To compare the rates of CTC response by treatment arm..
- 7) To explore the molecular mechanisms within the androgen receptor pathway by determining the levels of CXCR4 and TMPRSS2-ERG expression, androgen metabolism enzymes, androgen receptor variants, and length of CAG repeats within the androgen receptor gene, and to associate them with the primary endpoint.

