11.6 Analysis

11.6.1 For the primary objective, the binary endpoint (PSA remission at month 7, yes/no) will be summarized with its point estimate (an occurrence rate), and 2-sided Wilson type 95% confidence interval (CI). This analysis will be performed two ways: a) for all randomized patients (the intention to treat subset); and b) for all r-e patients (the per protocol subset). PSA response rates will be compared by treatment arm in a stratified logistic regression model, with stratification by race (AA, Other) and bone pain (yes, no).

11.6.2 All binary endpoints in secondary objectives 1-2 and 4-7, will be summarized with point estimates (occurrence rates), and 2-sided Wilson type 95% CIs. The analysis of toxicity rates will be performed using only the toxicity-evaluable (t-e) patients (defined in Section 8.11).

11.6.3 For secondary objective 4, the grade of each type of toxicity (an ordinal categorical variable) will be summarized with 1-way frequency distributions. A similar descriptive analysis will be performed for any correlatives in secondary objective 7 to be assayed by IHC, resulting in ordinal categorical variables (intensity levels of 0, 1+, 2+, or 3+).

Dichotomized versions (e.g., the occurrence rate of Grade 3-4 neutropenia) will be summarized as described in Section 11.6.2. A similar descriptive analysis will be performed for the presence/absence of any correlatives in secondary objective 7 to be assayed by IHC, with presence defined as intensity level of 1+ through 3+.

For any correlatives in secondary objective 7 that are assayed in both pre- and post-treatment prostate tumor tissues, the change in IHC expression level will be described using a 2-way frequency distribution. If the effective sample size appears to be sufficient relative to the size of the 2-way table, the association of these paired variables can be tested with the exact version of McNemar's test.

11.6.4 All censored time-to-event distributions for secondary objectives 3 and 5 will be estimated with standard Kaplan-Meier (K-M) methodology. Point and CI estimates of the median and various time point-specific rates will be derived from the K-M life table. The censored K-M distributions will be compared with the log-rank test, stratified by race (AA, Other) and bone pain (yes, no).

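### Section 11.6.3 names exact McNemar to test 'association' in paired four-level IHC scores, but it is a 2x2 test of change and the plan does not tie it to a 2x2 version

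*Combined protocol and SAP*

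**What the plan says.** Section 11.6.3 classes the correlatives assayed by IHC as ordinal, graded 0, 1+, 2+ or 3+. Section 8.14 agrees: "Scoring will be between 0 to 3 and will be done by 2 independent experienced investigators". A separate paragraph of 11.6.3 defines a dichotomy for descriptive summary, with 0 as absent and 1+ to 3+ as present.

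For markers assayed both before and after treatment, 11.6.3 says that "the change in IHC expression level will be described using a 2-way frequency distribution". A test is then allowed under a condition: "If the effective sample size appears to be sufficient relative to the size of the 2-way table", then "the association of these paired variables can be tested with the exact version of" McNemar's test.

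The section does not say whether the tested table is the four-level one or the absent/present one. It names no extension of McNemar to larger tables and no paired test for ordinal scores.

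The analysis belongs to secondary objective 7 (section 11.2), which begins "To explore the molecular mechanisms within the androgen receptor pathway". The number of pairs is not stated. Inclusion criterion 12 in section 4.1 says: "Post therapy biopsy is optional".

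**The concern.** Two things do not fit together.

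- **Table and test.** A pre-by-post table of a four-level score is 4x4. Exact McNemar is a binomial test on the two discordant cells of a 2x2 table. The condition about the size of the table also suggests that it may be larger than 2x2. An analyst following the text would have to decide, possibly after seeing the data, whether to dichotomise or to substitute another test.
- **Target and test.** McNemar asks whether the marginal proportions differ before and after treatment. It does not ask whether a patient's two values are related. Sections 11.6.6 and 11.6.7 use 'association' in its ordinary sense, so a reader could take a McNemar p-value as evidence of correlation between the paired scores.

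At stake is how change in CXCR4, ERG and the androgen biosynthesis enzymes is tested when paired tissue exists. If the analyst makes the test fit by using absent/present, a fall from strong to weak staining contributes nothing to it.

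**Working it through.** **Plan's own figure.** The plan gives no sample size, power or alpha for the paired IHC test, so there is nothing to reproduce for it. The 41 per arm in section 11.5.1 concerns the primary endpoint and does not bear on this point.

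**Inputs from the plan.** Four score levels and the 0 versus 1+ to 3+ dichotomy (11.6.3).

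**Assumed inputs.** The pre/post tables below are invented for illustration, with 20 pairs each.

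**Formulas.**
- Exact McNemar, two-sided: with b and c discordant pairs in the 2x2 table, a binomial test of b out of b + c at 0.5. If b + c = 0, p = 1. If all m discordant pairs go one way, p = 2 x 0.5^m.
- Exact sign test on the four-level score: the same binomial test on the counts of rises and falls.
- Exact signed-rank: when all m non-zero differences go one way, also p = 2 x 0.5^m.
- Association: Fisher's exact test on the absent/present table.

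**Tables.**
1. No pair changes; 5 pairs at each level. 2x2 counts: 5 absent both times, 15 present both times, none discordant.
2. Ten pairs fall from 3+ to 1+; unchanged are 3 at 0, 2 at 1+ and 5 at 2+. 2x2 counts: 3 absent both times, 17 present both times, none discordant.
3. Ten pairs fall to 0 (3 from 1+, 3 from 2+, 4 from 3+); unchanged are 5 at 0, 2 at 1+, 2 at 2+ and 1 at 3+. 2x2 counts: 5 absent both times, 5 present both times, 10 present then absent.

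| Table | McNemar, absent/present | Fisher, association | Sign test, four levels |
|---|---|---|---|
| 1 | 1.00 | 0.00006 | 1.00 |
| 2 | 1.00 | 0.0009 | 0.002 |
| 3 | 0.002 | 0.27 | 0.002 |

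**Reading.** Tables 1 and 3 show that McNemar does not test association: with perfect association and no change it gives 1.00, and with clear change and weak association it gives 0.002. Table 2 shows the loss from dichotomising: there are no discordant pairs, so p = 1, against 2 x 0.5^10 = 0.00195 for the sign and signed-rank tests.

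**Range over where the change occurs.** Keep 10 of 20 pairs falling and let k of them fall to 0. The sign test stays at 0.002. McNemar on absent/present gives 2 x 0.5^k for k of 1 or more:
- k = 0: 1.00
- k = 2: 0.50
- k = 4: 0.125
- k = 6: 0.031
- k = 8: 0.008
- k = 10: 0.002, so the two tests agree

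**Range over the number of pairs.** The smallest two-sided p that the sign or signed-rank test can reach with m changed pairs is 2 x 0.5^m: 0.125 for m = 4, 0.031 for m = 6, 0.002 for m = 10. Section 10.7 mentions paired biopsies from four patients for one add-on enzyme assay, with more possible. If only four pairs existed, the choice of test would hardly matter.

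**The case against.** The case for leaving the section alone has real substance.

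- **Purpose.** A reader might infer that McNemar does not fit the purpose of the analysis. The sentence just before gives that purpose as describing change in expression level, and McNemar does test change. The misfit is with the word 'association' and with the four-level scale. This part of the objection stands.
- **A valid 2x2 version exists.** A reader might infer that the test cannot be run. Exact McNemar is valid on the absent/present version defined in the same section, and symmetry tests extend McNemar to larger tables. What remains is that the plan neither links the test to absent/present nor names an extension.
- **Information loss.** A reader might infer that the plan throws away most of the change. The full cross-tabulation is the planned description and would show every shift, and section 11.6.5 summarises QPCR levels of ERG and CXCR4 as continuous variables. The documents give no IHC distribution from which to judge how much a dichotomised test would miss. The loss is confined to the test, and its size is unknown.
- **Consequence.** The test is permitted, not required. Associating markers with the primary endpoint has its own method in 11.6.6, exact logistic regression, with interpretation limited to direction, magnitude and precision. This stands, and it is why the point is minor.
- **Choice of remedy.** Signed-rank ranks the sizes of score differences and so treats the steps between grades as comparable, which an ordinal scale does not guarantee. This stands; a sign or marginal-homogeneity test avoids that assumption.

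**Conclusion.** The point holds as a specification fault of low severity. The named test is a 2x2 test of marginal change, while the text around it describes a four-level paired score and calls the target 'association'. The one 2x2 version in the plan is not tied to the test and cannot register shifts among 1+, 2+ and 3+.

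The size of the effect depends on data that the documents do not give. The contrast of p = 1 with p = 0.002 rests on an assumed table in which no change crosses zero, which is the extreme case. The gap closes as more changes cross zero, and it matters little with very few pairs. The documents do not support reading this as a wrong test of treatment effect on the markers, or as a threat to the trial's conclusions: it touches an optional test within an exploratory objective that depends on optional biopsies. The primary analysis and the sample size are unaffected.

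**What to change.** In section 11.6.3:

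1. Replace 'association' with 'change' in the sentence that names McNemar's test.
2. State that change in the four-level score will be tested with one named exact paired ordinal test: an exact marginal-homogeneity test for ordered categories or an exact sign test. Signed-rank is acceptable if the plan says that score steps are treated as comparable.
3. Limit exact McNemar to the absent/present version (0 against 1+ to 3+).

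The cost is a sentence or two in the SAP. Data collection, sample size and the primary analysis do not change. The gain is that the choice of test is fixed before the paired scores are seen.

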All lesions (or sites of disease) not identified as target lesions, including pathological lymph nodes and all non-measurable lesions, should be identified as non-target lesions and be recorded at baseline. Measurements of these lesions are not required and they should be followed as 'present', 'absent' or in rare cases, 'unequivocal progression'.

Evaluation of target lesions

Complete Response (CR): Disappearance of all target lesions. Any pathological lymph nodes (whether target or non-target) must have reduction in short axis to <10 mm.

Partial Response (PR): At least a 30% decrease in the sum of diameters of target lesions, taking as reference the baseline sum of diameters.

Progressive Disease (PD): At least a 20% increase in the sum of diameters of target lesions, taking as reference the smallest sum on study (this may include the baseline sum). The sum must also demonstrate an absolute increase of at least 5 mm.

Stable Disease (SD): Neither sufficient shrinkage to qualify for PR nor sufficient increase to qualify for PD.

Confirmation

In non-randomized trials where response is the primary endpoint, confirmation of PR and CR is required to ensure responses identified are not the result of measurement error. This will also permit appropriate interpretation of results in the context of historical data where response has traditionally required confirmation in such trials. However, in all other circumstances, (i.e., in randomized phase II or III trials or studies where stable disease or progression are the primary endpoints), confirmation of response is not required since it will not add value to the interpretation of trial results. However, elimination of the requirement for response confirmation may increase the importance of central review to protect against bias, in particular in studies which are not blinded. In the case of SD, measurements must have met the

SD criteria at least once after study entry at a minimum interval (in general not less than 6–8 weeks) that is defined in the study protocol.

8.1 Primary Endpoint:

The proportion of patients on either arm achieving a PSA nadir of 4 or less (< 4 ng/ml) at month 7 of protocol therapy.

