8.3 Duration of overall response

The duration of overall response is measured from the time measurement criteria are met for CR/PR (whichever is first recorded) until the first date that recurrent or progressive disease is objectively documented (taking as reference for progressive disease, the smallest measurements recorded since the treatment started).

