8.4 Duration of stable disease

Stable disease is measured from the start of the treatment until the criteria for progression are met, taking as reference the smallest measurements recorded since the treatment started. Tumor evaluations are recommended every three cycles while on protocol therapy and then as clinically required by the treating physician.

8.5 Time to Treatment Failure:

From date of registration to date of progressive disease, or date patient is taken off study for any reason. All patients, regardless of the number of completed cycles of therapy, will be included for toxicity evaluation. All subjective toxicities encountered during the study will be evaluated according to the NCI toxicity criteria. Objective toxicities will be based upon the greatest severity that occurred at any time during a treatment cycle and not on the severity noted at the beginning of the next cycle.

8.6 Time to Progression:

From date of registration to date of progressive disease, defined as either progression of measurable disease by RECIST 1.1 criteria, or progression of bone metastases or occurrence of new skeletal related event or by PSA per PCWG 2 criteria [Appendix B].

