11.3 Endpoints

11.3.1 For the primary objective, the binary endpoint will be the achievement of PSA remission at month 7 (yes or no). This endpoint is described in the Study Schema and in Section 8.1.

11.3.2 For secondary objective (1), the primary endpoint is described in the Study Schema and in Section 8.1. The two race groups to be compared are AA vs Other, as described in the Study Schema.

11.3.3 For secondary objective (2), the endpoints will be the achievement of:
a) measurable disease response (yes or no), (defined in Sections 8.0 and 8.9); and
b) PSA response (as defined in Section 8.2).

11.3.4 For secondary objective (3), the endpoints will be the length of censored:
a) duration of overall response (RD), as defined in Section 8.3;
b) duration of stable disease (SDD), as defined in Section 8.4;
c) time to treatment failure (TTF), as defined in Section 8.5;
h) time-to-progression (TTP), as defined in Section 8.6;
i) TTP in patients with bone metastases, as defined in Section 8.7;
j) progression-free survival (PFS), as defined in Section 8.8; and
k) overall survival (OS), as defined in Section 8.9.

11.3.5 For secondary objective (4), the endpoints will be the occurrence rate of each specific type of toxicity observed (defined in Section 6.0) and treatment arm (A or B, defined in Study Schema, Section 5.3, and Section 11.1).

11.3.7 For secondary objective (5), the endpoints will be the occurrence rate of SRE (defined in Section 8.12), the distribution of time until SRE, and treatment arm (A or B). Follow-up for SRE will continue until SRE, PSA progression, or death, whichever occurs first.

11.3.8 For secondary objective (6), the endpoints will be the occurrence rate of CTC response (defined in Section 8.13), and treatment arm (A or B).

11.3.9 For secondary objective (7), the endpoints will be the expression levels of the selected genes or enzymes stated in Section 11.2, length of CAG repeats, and the primary endpoint of PSA remission at month 7 (yes or no). The correlates are defined and described in Section 10.0. The expression level of those biomarkers will be determined in both pre- and posttreatment prostate tumor tissues, and in post-treatment bone biopsy samples

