11.5 Sample Size Determination

The assumptions made to permit sample size determination are:

- 1) The population reference value of the proportion of patients achieving (and then sustaining) $PSA \leq 4$ ng/ml (4 or less) within 7 months of starting therapy is 50% for men on the standard (i.e., control arm, or Arm B) therapy of LHRH agonist + bicalutamide;
- 2) The hypothesized rate of patients achieving (and then sustaining) $PSA \leq 4.0$ within 7 months of starting therapy on the experimental arm (i.e., enzalutamide, or Arm A) is 75%;
- 3) significance level of 0.10, one-sided (in view of the directional hypothesis);
- 4) power = 0.80;
- 5) balanced (i.e., 1:1) randomization.

11.5.1 Under those assumptions, the required sample size is N=41 response-evaluable (r-e) patients (defined in Section 8.10) on each arm. That calculation used the method of Fleiss et al [42], and was performed with the nQuery Advisor software, Version 7.0. The total sample size required is 82 patients. Allowing for up to 10% of patients who might not become r-e, up to 46 patients per arm (a total of 92 patients) may need to be enrolled.

11.5.2 Enrollment to this study is expected to be approximately 25-30% AA (from all participating institutions). For better generalization of our study results, we seek a minimum accrual of 25 (approximately 30%) evaluable AA patients. To achieve that goal, it may become necessary to close accrual to non-AA patients at some point during the study. Let p = the primary endpoint (the proportion of patients achieving $PSA \leq 4.0$ within 7 months). With 25 AA patients, p can be estimated to within 0.183 of its true value with 95% confidence, regardless of the level of p .

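### Duration of response is tested between arms by log-rank, but only responders have a duration, so the comparison is not randomised; the population for duration of stable disease is not stated.

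*Combined protocol and SAP*

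**What the plan says.** Secondary objective 3 in section 11.2 reads "To compare each of 7 time-to-event endpoints by treatment arm". RD and SDD head the list, and section 11.3.4 treats both as censored times: "For secondary objective (3), the endpoints will be the length of censored".

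Section 8.3 fixes the RD clock: "The duration of overall response is measured from the time measurement criteria are met for CR/PR (whichever is first recorded"). Section 8.4 defines SDD differently: "Stable disease is measured from the start of the treatment until the criteria for progression are met". It does not say which patients have an SDD. Under the response criteria in section 8.0, stable disease is itself a post-baseline category: "Neither sufficient shrinkage to qualify for PR nor sufficient increase to qualify for PD".

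Section 11.6.4 covers the whole list without exception: "All censored time-to-event distributions for secondary objectives 3 and 5 will be estimated with standard Kaplan-Meier (K-M) methodology", followed by "The censored K-M distributions will be compared with the log-rank test, stratified by race (AA, Other) and bone pain (yes, no"). Nothing in the document makes RD or SDD descriptive only. The limit on interpretation in 11.6.6 and 11.6.7 applies to correlative markers. The non-definitive label in 11.4.1 applies to the primary outcome.

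**The concern.** Randomisation makes the two arms comparable. It does not make the responders in one arm comparable with the responders in the other. If enzalutamide raises the response rate, Arm A's responders include men who would not have responded on Arm B. Where response goes with good prognosis, those extra responders have poorer prognosis on average and shorten Arm A's typical duration, even if the drug does nothing to duration. The trial's rationale supposes a link of this kind: section 2.0 cites median survival of 13, 44 and 75 months by depth of PSA nadir.

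The stratified log-rank test conditions on race and bone pain only, so other prognostic differences between the responder groups remain. At stake is a secondary p-value, and a pair of medians by arm, that could seem to contradict a favourable primary result because of selection alone.

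**Working it through.** **1. The plan's own figure.** The documents give no figure for RD or SDD; the only sample size is for the primary endpoint. Inputs from 11.5: the control rate "is 50% for men on the standard (i.e., control arm, or Arm B) therapy", 75% on Arm A, one-sided alpha 0.10, power 0.80.

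- Uncorrected n = [1.2816 × √(2 × 0.625 × 0.375) + 0.8416 × √(0.25 + 0.1875)]² / 0.25² = (0.877 + 0.557)² / 0.0625 = 32.9.
- With continuity correction: (32.9/4) × [1 + √(1 + 4/(32.9 × 0.25))]² = 40.5, so 41 per arm.
- 41/0.90 = 45.6, so 46 enrolled per arm.

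The stated 41 and 46 reproduce. They have no bearing on RD.

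**2. Who has an RD.** By 8.3, patients with CR or PR only. If all 46 per arm had measurable disease and responded at 75% and 50%, that would be 34.5 and 23 patients. With 18 measurable per arm it is 13.5 and 9; with 9 per arm, 6.75 and 4.5. The PSA-remission rates are a stand-in, since no RECIST rate is given.

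**3. Size of the selection effect.** Assumptions, none from the documents: a standard normal prognosis U; a response tendency with correlation ρ to U, cut so that 75% or 50% respond; exponential duration with scale 18 × exp(0.6U) months, identical in both arms.

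- Mean response tendency among responders = φ(z)/p. Arm A: 0.3178/0.75 = 0.424. Arm B: 0.3989/0.50 = 0.798. Difference 0.374.
- Shift in mean log duration = 0.6 × ρ × 0.374, which is 0.112 at ρ = 0.5 and 0.202 at ρ = 0.9. Arm B's responders therefore last exp(0.112) = 1.12 to exp(0.202) = 1.22 times as long, with no drug effect.
- Approximate median = 18 × ln 2 × exp(0.6 × ρ × mean tendency). At ρ = 0.5: 14.2 (A) vs 15.8 (B) months. At ρ = 0.9: 15.7 vs 19.2. Simulation gives 14.0 to 15.5 vs 15.9 to 19.4.

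The shift does not depend on the number of patients.

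**4. How often the test misleads.** Same model, censoring uniform over 7 to 44 months, unstratified log-rank, no drug effect on duration. Share of trials declaring Arm A worse (nominal 2.5%):

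| Setting | Arm A falsely worse |
|---|---|
| 46 measurable per arm, 75% vs 50%, ρ 0.5 to 0.9 | 4.5 to 6.9% |
| 18 per arm | 3.4 to 5.0% |
| 9 per arm | 2.9 to 3.7% |
| 46 per arm with ρ = 0, or equal response rates, or all randomised patients | 2.1 to 2.7% |

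At one-sided 0.10, the level that 11.5 sets for the primary endpoint, the first row becomes about 16 to 23% against 10%.

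**5. SDD, if restricted to stable-disease patients.** A separate simulation (18-month median to progression, assumed stable-disease rates of 15% in Arm A and 30% in Arm B, no drug effect) gives a hazard ratio A:B of 1.24 at ρ = 0.5 and 1.40 at ρ = 0.8. RD in the same runs gives 1.15 and 1.26. All randomised patients give 1.00 to 1.02. If SDD is read over all patients, it runs from treatment start to progression, is close to TTP, and has no such bias.

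**The case against.** Four points can be made for the plan.

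- **The responder set is probably small.** Section 8.7 says that most patients have bone metastases, which are not measurable. CT is optional at entry (4.1, item 8) and done only where needed (7.0, note 3). One eligibility route requires no visceral and fewer than four bone metastases (4.1, item 14). This stands, and it is why the 4.5 to 7% figure is an upper illustration. With 9 measurable patients per arm and the planned four strata, simulated as non-prognostic, the rate is 2.6 to 2.8%. That reflects lost power: the shift in step 3 is unchanged and would still appear in the medians.
- **The direction is conditional.** This stands. With equal response rates or no link to prognosis there is no bias. With rates of 60% vs 50% and 46 per arm, the false rate is only about 3 to 4%.
- **SDD may cover everyone.** This also stands. A reader might infer that SDD is necessarily an outcome-selected comparison. Section 8.4 does not say so.
- **It is a screening trial with other endpoints.** TTF, TTP, PFS and OS run from registration (8.5, 8.6, 8.8, 8.9) and already give comparisons not selected by response. That limits the consequence, but a relaxed error rate does not correct a bias, and 11.6.4 still produces the RD test.

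**Conclusion.** The point holds for RD by definition: the planned log-rank test compares groups formed after randomisation, and nothing in the document restores comparability. For SDD it holds only under one of two readings, so the defect there is an unstated population.

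The size cannot be fixed from the documents. The figures rest on PSA-remission rates standing in for RECIST response, an assumed correlation of 0.5 to 0.9, an assumed spread of prognosis and an unstratified test. The 2.5% reference is conventional, since the plan sets no level for secondary endpoints. On that basis a false finding against Arm A occurs in about 4.5 to 7% of trials if all 46 per arm are measurable, and about 3 to 5% with 9 to 18.

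A reader might infer that the trial is likely to report a falsely shorter duration on enzalutamide, or that its main conclusion is at risk. Neither follows. The bias is a conditional tendency of modest size, and the primary analysis and sample size are untouched.

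**What to change.** - In 11.6.4, exclude RD from the log-rank comparison, and SDD too if it is restricted to stable-disease patients. Report them by arm with Kaplan-Meier estimates, and say that the groups compared are not randomised. Align objective 3 in sections 1.0 and 11.2.
- In 8.4, state who has an SDD. If it is everyone, say how it differs from TTP.
- State that between-arm inference on time-to-event outcomes rests on TTP, PFS, TTF and OS, all measured from registration.
- If duration must be compared, use mean time in response, up to a fixed horizon, over all randomised patients with measurable disease at baseline, counting non-responders as zero. This combines response rate and duration, so it should be labelled as such.

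The cost is wording and at most two secondary p-values. No new data or patients are needed.
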